### 3 Aim and Objectives

### 3.1 Aim

This study aims to measure the change in Quality of Life (QOL) following an interaction with SYD, a personalised preventative mHealth partner. Measures of mental health (stress, anxiety and depression) will also be tracked as a way to assess the wellbeing potential of this non-clinical intervention. At this point, physical parameters are not formally the focus of any change such as blood pressure or weight, but these data points are already on the platform to receive data in the future.

Title: Pilo	Title: Pilot evaluation of a personalised, prevention mHealth partner, SYD, and its impact on Quality of Life of NHS staff							
Authors	[name], [name], [name], [name], [name]	Ver.	2.0	Date Authorised	13/04/2022	Page 9 of 24		

#### 3.2 Primary objectives

Determine the impact of SYD on Quality of Life of NHS Staff over 3 months, as measured through:

- 1. WHO Quality of Life-BREF (WHOQOL-BREF) survey (Global QOL)
- 2. EuroQoL EQ-5D-5L (Health-related QOL)

### 3.3 Secondary objectives

- 1. Determine the efficacy of SYD in reducing levels of stress, anxiety and depression, as measured through the Perceived Stress Scale (PSS-4) and Hospital Anxiety and Depression Scale (HADS).
- 2. Determine user satisfaction and engagement with SYD
- 3. Determine the persistence of primary endpoint changes over 6-month time frame

### 3.4 Compliance with regulations and Guidance

As defined in the European Commission Green Paper (EC, 2014), as an app providing lifestyle guidance and prevention information only, SYD is considered a mobile Health (mHealth) product. SYD is compliant with the legislative requirements applicable to all mHealth products outlined in the Green Paper framework, including relevant data protection and data security regulations.

As a software intended for lifestyle and wellbeing purposes SYD is not classed as a medical device under EU Medical Device Regulation 2017/45 and as defined by the Medicines and Healthcare Products Regulatory Agency (MHRA) guidance on the classification of stand-alone software including apps (MHRA, 2018); therefore it does not require CE marking.

The design of this trial follows the principles of best practice standards for evaluating effectiveness of Digital Health Technologies (DHTs) as outlined in National Institute of Health and Clinical Excellence (NICE)'s Evidence Standards Framework for Digital Health Technologies (2019) developed in collaboration with NHS England, NHS Digital and other stakeholders. The framework provides a functional categorisation of DHTs based on their clinical impact and potential risk. Using this framework, SYD is classified as 'Tier 3a: DHTs for preventing and managing diseases' for which interventional trial designs incorporating a comparison group are recommended as best practice method of evaluating effectiveness.

This protocol was developed with a multidisciplinary team (MDT) approach of consultants, nurses, physician associates and researchers in order to ensure the best possible outcome for the study participants.

### 3.5 Trial Design

#### **Design considerations:**

The trial is designed carefully and deliberately to fully and prospectively elucidate all elements of comparison of the impact of SYD. Participants would be randomly assigned to one of the two trials cohorts (PHE, 2020).

For cohort one, the study allows data collection as part of a 'Before and After Study', with SYD as the intervention provided to participants, to engage with, for 3 months as a minimum.

Additionally, by having a further cohort (cohort two) without SYD being engaged for the first 3 months, the study allows 'Case Controlled' cross comparisons between the two cohorts.

Title: Pilot	Title: Pilot evaluation of a personalised, prevention mHealth partner, SYD, and its impact on Quality of Life of NHS staff							
Authors	[name], [name], [name], [name], [name]	Ver.	2.0	Date Authorised	13/04/2022	Page 10 of 24		

Additionally, by collecting data on the first cohort further to 6 months, we can review persistence of effects from 3 to 6 months of SYD and whether participants voluntarily continue using SYD or not beyond the primary endpoint.

Bringing on board the second cohort to have SYD switched on after 3 months, allows a comparison within this cohort 'Before and After' at a different time-point to the switch on for cohort one. This allows for any effects of SYD to be evaluated as COVID-19 levels themselves change over time.

Meanwhile comparing the two cohorts after the second cohort is exposed to SYD will allow comparisons of an early (in second cohort) versus a more experienced group (first cohort) using SYD contemporaneously.

We feel these design elements have not been considered for previous mHealth interventions and given the nonblinded nature of this trial design, it is imperative to establish the exact value of SYD itself to remove temporal, experiential or environmental comparisons.

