#### Participants:

NHS staff, 18 years and over, who took part in the 'Psychological impact of the Coronavirus (COVID-19) pandemic and experience: An international survey' study (PIoC19 study; IRAS Project ID 282858; REC reference 20/HRA/1934), and provided informed consent to be contacted for future versions of the study ( $n \approx 3500$ ), will be invited to participate in the 'SYD for NHS' trial via email. Once this pool of potential participants is given the opportunity to participate, then the study will be offered to all NHS organisations who may wish to participate in the trial as Participant Identification Centres (PIC). PIC sites will be provided with an open link of the study website to share with their current staff.

Any interested potential participants will be directed to the study website and asked to familiarise themselves with the information provided in the Patient Information Sheet. Those participants who are interested to take part in the study will be asked to complete questions to confirm eligibility, following which they will be asked to consent to undertake a Hospital Anxiety and Depression Scale (HADS) test. Optional consent to be contacted for future ethically approved research in the field of mental health and digital health technologies will be sought. Potential participants who score between 8-14 inclusive will be eligible, as these scores indicate individuals most likely to benefit from interventions of wellbeing like SYD and to be considered safe as higher scores may indicate depression/anxiety levels needing formal psychological evaluation. Participants with HADS scores 15 and over will be advised that they might need to contact their GP for further support. Individuals with low levels of anxiety often do not engage well with wellbeing measures (Singer et al. 2009).

Following confirmation of informed consent, and confirmed eligibility from the screening questionnaire, participants will be randomised 1:1 to one of two groups: Control Group and Intervention Group. People considered clinically extremely vulnerable for COVID-19, are excluded to avoid conflict with government advice. (https://www.gov.uk/government/publications/guidance-on-shielding-and-protecting-extremely-vulnerable-persons-from-covid-19/guidance-on-shielding-and-protecting-extremely-vulnerable-persons-from-covid-19)

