#### 8 Study duration

The recruitment phase of the study is expected to last for up to 12 months.

The total duration of the trial data collection will be from the date of randomisation of the 1st participant to the date on which the last randomised participant reaches 6 months follow-up time point (including two weeks grace to allow timely response).

Therefore, the key dates of the study are:

- Recruitment start date: 1st June 2021
- Recruitment end date: 15th April 2022
- Study data collection end date: 29th October 2022

Participants in the Control Group (Group B) will complete baseline assessments (Month 0), monthly assessments - control data (Months 1-3) and receive intervention (Months 4-6) / complete follow up assessment (Month 6).

Participants in the Intervention Group (Group A) will complete baseline assessments (Month 0), receive intervention / complete monthly assessments in (Months 1-3). A final assessment will be performed after 3 months (Month 6) to assess longer term effects of the intervention.

We aim to undertake the primary analysis after the last participant in the Intervention Group has reached Month 3 data capture point and completed final data entry. Further analysis to assess longer term effects of the intervention will be undertaken after the final study completion.

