### 10 Statistics and data analysis

### **10.1 Data handling and analysis**

Study data will be collected via the Qualtrics online website built for this study. The Qualtrics survey software has advanced analytics tools built online and analyses will only be descriptive. Data will be analysed by Investigators at the Sponsor organisation (Southern Health NHS Foundation Trust). No data queries will be raised for participants.

Primary endpoint analysis will be undertaken using data collected throughout a period of 3 months of SYD application usage by the study participants. Further analysis of longer-term effects will be undertaken at 6 months after the participant first interacted with the SYD application.

WHOQOL-BREF surveys will be scored according to the general guidelines (World Health Organization, 1996), deriving scores for the 4 main domains (Physical health, Psychological, Social relationships and Environment).

EQ-5D-5L surveys will be scored according to the general guidelines (Herdman et al., 2011), deriving scores for the 5 main domains of the instrument (Mobility, Self-Care, Usual Activities, Pain/Discomfort and Anxiety/Depression), and

Title: Pilot	Title: Pilot evaluation of a personalised, prevention mHealth partner, SYD, and its impact on Quality of Life of NHS staff								
Authors	[name], [name], [name], [name], [name]	Ver.	2.0	Date Authorised	13/04/2022	Page 16 of 24			

SYD (See Yourself Differently) for NHS the 1-dimensional EQ VAS. An EQ-5D index value will be derived from EQ-5D-5L scores using the latest value set for England (Devlin et al., 2018).

PSS-4 scores will be derived according to the general guidelines (Cohen, 1988).

HADS scores will be subdivided into anxiety (HADS-A) and depression (HADS-D) subdomains and scored according to general guidelines (Zigmond et al., 1983).

WHOQOL-BREF, 5Q-5D-5L, EQ-5D index, HADS-A, HADS-D and PSS-4 scores will be modelled using linear mixed effects models. These models will be used to test the effect of group, time of measure and app-related metrics such as type of recommendations done by participants and level of interaction with the SYD app. Baseline characteristics of participants will be used to adjust the models. Imputation procedures will be used to impute missing values where deemed plausible. Effect size measures and p-values will be reported for all group comparisons. The Null hypothesis is of no significant change in Quality of Life.

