### **15 Protocol Deviations**

A study related deviation is a departure from the ethically approved study protocol or other study document or process (e.g. consent process or administration of study intervention) or from Good Clinical Practice (GCP) or any applicable regulatory requirements. Any deviations from the protocol will be documented in a protocol deviation form and filed in the study master file.

Of note, SYD might have routine research updates for the duration of the trial, namely to the recommendations it provides to its users. This material is continually reviewed by a clinical advisory group and updated if evidence is considered sufficiently strong to indicate benefit to its users or employers.

Title: Pilot evaluation of a personalised, prevention mHealth partner, SYD, and its impact on Quality of Life of NHS staff							
Authors	[name], [name], [name], [name], [name]	Ver.	2.0	Date Authorised	13/04/2022	Page 19 of 24	

The reporting procedure for any potential protocol breaches will be for the study team to report to [name] at Southern Health NHS Foundation Trust. Any potential breach will be assessed by [name] and at least 2 of the following from [name], [name], [name] and [name] to assess whether a non-compliance / deviation may be a potential serious breach. If [name] is unavailable, [name] or [name] will deputise as lead for timely evaluation of protocol breaches.

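### Cohort two's later before-after change cannot show SYD's effect at different COVID-19 levels: the change is uncontrolled and the two cohorts' switch-on dates largely overlap

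*Protocol*

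**What the plan says.** - Protocol section 3.5, Design considerations: "Bringing on board the second cohort to have SYD switched on after 3 months, allows a comparison within this cohort 'Before and After", at a time-point other than cohort one's. The purpose follows at once: "This allows for any effects of SYD to be evaluated as COVID-19 levels themselves change over time". The section closes by saying that, as the trial is not blinded, SYD's own value has to be separated from influences of time, experience and environment.
- Section 3.5, Participants: "participants will be randomised 1:1 to one of two groups: Control Group and Intervention Group".
- Section 8: "The recruitment phase of the study is expected to last for up to 12 months". The key dates are "Recruitment start date: 1 st June 2021" and a close of recruitment on 15 April 2022.
- Section 6: the Intervention Group is invited to use the app at Baseline and the Control Group at Month 4. Section 3.5 (Participants) also gives Month 4, while its Design considerations speak of switch-on after 3 months.
- Sections 6 and 7: both groups are assessed at Months 0, 1, 2, 3 and 6, with nothing at Months 4 or 5.
- Section 10.1, on the mixed models: "These models will be used to test the effect of group, time of measure and app-related metrics". Adjustment for baseline characteristics is added. Neither calendar date nor COVID-19 level is named.
- Section 15: "SYD might have routine research updates for the duration of the trial".

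**The concern.** To learn how SYD works at different COVID-19 levels, one needs treated and comparable untreated people at each level. Section 3.5 relies instead on one cohort's change after a later switch-on. That would help only if the later switch-on placed cohort two in a clearly different stretch of the pandemic, and if nothing else changed between its before and after points. Neither condition looks safe. Entry is rolling, and the delay is counted from each person's entry, so the delay is fixed in study time and not in calendar time. A before-after change also has no untreated comparator.

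At stake is one secondary inference. Section 1 names the design as both a randomised trial and a controlled before-and-after study, so the before-after results are likely to be reported. A change, or a gap between the two cohorts' changes, could then be presented as evidence about COVID-19 when it has other sources.

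**Working it through.** **Inputs (section 8).** Recruitment runs from 1 June 2021 to 15 April 2022, with six months of follow-up and two weeks' grace. As a check, 15 April 2022 + 6 months + 14 days = 29 October 2022, which is the stated end of data collection. These dates are used although sections 1 and 20 put the end of trial at 31 March 2022.

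**Switch-on windows.** Cohort one's window is the recruitment window: 319 days, counting both ends. Cohort two's is the same window moved by the delay. Overlap = shared days / 319.

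| Delay | Cohort two's window | Shared days | Overlap |
|---|---|---|---|
| 3 months | 1 Sep 2021 to 15 Jul 2022 | 1 Sep to 15 Apr = 227 | 227/319 = 71% |
| 4 months | 1 Oct 2021 to 15 Aug 2022 | 1 Oct to 15 Apr = 197 | 197/319 = 62% |

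If recruitment took the full 12 months that section 8 allows, the shares would be (12 − 3)/12 = 75% and (12 − 4)/12 = 67%.

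**Before-after windows.** Cohort one's Month 0-3 changes span 1 June 2021 to 15 July 2022 (410 days). Cohort two's Month 3-6 changes span 1 September 2021 to 15 October 2022. They share 1 September 2021 to 15 July 2022, which is 318 days: 318/410 = 78%.

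**From days to participants.** The protocol gives no accrual curve. If a fraction f of cohort one enters in the first 3 months, the share of cohort one starting on or after cohort two's first switch-on (3-month delay) is 1 − f. Uniform accrual gives f = 92/319 = 0.29 and a share of 0.71. Assumed values of f = 0.5, 0.7 and 0.9 give 0.5, 0.3 and 0.1.

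**What else differs between the two changes.**

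| | Cohort one | Cohort two |
|---|---|---|
| Before point | Month 0 | Month 3 (last assessment before switch-on) |
| Study assessment rounds completed earlier | none | Months 0, 1 and 2 |
| After points up to the end of the window | Months 1, 2, 3 | Month 6 only |
| Time on SYD at the last after point | 3 months | 3 months (switch-on after 3 months), or 2 if Month 4 means four months from entry |
| App content, for two people entering on the same day | as at entry | as 3 to 4 months later |

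Each row after the first is a possible source of difference that does not depend on COVID-19 level.

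**What the randomised part already supplies.** Month 1-3 assessments fall between 1 July 2021 (first entry + 1 month) and 15 July 2022 (last entry + 3 months), about 12.5 months. Throughout that span, users of SYD and untreated controls are followed side by side.

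**The case against.** The case for leaving the text alone has several parts.

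- **Section 3.5 describes a comparison within cohort two.** It never says that the difference between the cohorts' changes will be read as a COVID-19 effect. No objective or endpoint concerns COVID-19, and section 3.9 calls the trial a pilot. This stands, and it limits the weight of the point. It does not make the within-cohort change informative, because that change has no untreated comparator.
- **Covariates and interaction terms are usual content of an analysis plan, and section 10.1 does not say that time of measure means study month only.** This stands for the bare absence of a calendar term. It does not cover section 3.5, where the protocol itself names the route to the COVID-19 question.
- **Rolling entry spreads both groups over the calendar, so the design does permit such an evaluation.** True, but through the randomised contrast and not through the route that section 3.5 gives.
- **Shared days are not shared participants.** Sections 3.5 and 4 describe an emailed pool first and other NHS organisations later, so early clustering is plausible and would reduce the overlap. The two cohorts' calendar periods would then be more distinct, but the differences in the second table would remain.

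A reader might also infer that selection on HADS makes cohort one's change contain regression to the mean that cohort two's escapes: "Potential participants who score between 8-14 inclusive will be eligible". The documents do not support giving that a size. Section 5.1 places a HADS at screening, section 5.2 the main consent after it, and section 6 another HADS among the baseline assessments on joining. Month 0 therefore appears to be a separate, later measurement. With a stable true score and independent error, the shift would then fall between screening and Month 0, outside both before-after changes. It could enter cohort one's change if the screening score were reused as Month 0, or if true levels drifted over the months. The source pool's mean, standard deviation and retest correlation are not given, so neither sign nor size can be fixed.

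**Conclusion.** The point holds in a limited form. The later before-after comparison in section 3.5 does not answer the question set for it there. On the stated dates the two switch-on windows share 71% (3-month delay) or 62% (4-month delay) of their days. The cohorts differ by a shift within one long window and do not represent distinct COVID-19 periods. An uncontrolled change, or a difference between two such changes, cannot separate COVID-19 level from time in study, repeated questionnaires, unequal follow-up after switch-on and possible content updates.

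The overlap in days rests only on the section 8 dates. Reading it as a share of participants needs uniform accrual. No size is claimed for any bias.

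A reader might go further and conclude that the estimate of SYD's effect is compromised. It is not: allocation is concurrent, both groups pass the same selection, and controls remain untreated through Month 3. The randomised comparison in Months 1-3 is unaffected.

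**What to change.** 1. **Section 3.5, basis of inference.** State that SYD's effect rests on the concurrent randomised difference in Months 1-3, and that the before-after changes in either cohort are descriptive. Remove the claim that cohort two's later change shows the effect as COVID-19 levels vary.
2. **COVID-19 question.** Add calendar period of assessment and a group-by-calendar-period term to the mixed model, limited to Months 1-3 and labelled exploratory. Define the periods before the data are examined. This needs the date of each assessment; the protocol does not say that it is kept, although an online survey can be assumed to provide it.
3. **Content updates.** Report the dates of SYD releases beside this analysis. Updates and recruitment source also move with calendar time, so the interaction cannot separate them from COVID-19 level. It does remove the differences in study time, repeated questionnaires and follow-up.
4. **Switch-on time.** Section 3.5 (Design considerations: after 3 months) and sections 3.5 (Participants) and 6 (Month 4) must be reconciled, because they decide how long cohort two has used SYD by Month 6.

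The cost is protocol wording and a few degrees of freedom, with no new visits or participants. The interaction will have low precision, and more so if entry is concentrated in the first months.

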Intervention Group: Participants in the Intervention Group will be asked to complete baseline assessments (Month 0) and download / interact with the SYD app (Months 0-3). Participants will complete monthly assessments for a period of 3 months (Months 1-3) to analyse the primary endpoint. A final assessment will be performed at Month 6, to monitor longer term effects of the intervention.

Control Group: Participants in the Control Group will be asked to complete baseline assessments (Month 0) and monthly assessments (Months 1-3) to provide control data in a comparable population. Participants will be advised that they will be invited to download / interact with the SYD app at Month 4 and that study data collection will continue for further 3 months thereafter (Months 4-6).

Title: Pilot	Title: Pilot evaluation of a personalised, prevention mHealth partner, SYD, and its impact on Quality of Life of NHS staff							
Authors	[name], [name], [name], [name], [name]	Ver.	2.0	Date Authorised	13/04/2022	Page 11 of 24		

Participants in both groups will continue to have access to SYD after the end of the trial for their personal use. The last data capture point will be 6 months after the last participant has entered the trial and completed data entry. Data for the purpose of the study will not be collected beyond the 6-month time point unless otherwise mandated by the data and safety monitoring committee for valid reasons.

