#### The following information will be collected from within the SYD app:

- 1. Participant characteristics including age, sex, demographics, self-assigned ethnicity and relevant medical conditions (e.g. Cardiovascular disease, Type 2 Diabetes, hypertension, etc.): will be collected when the participant first interacts with the SYD app
- 2. Self-rated measures related to 9 key dimensions of wellbeing (physical health, emotional health, financial health, purpose, social life, brain power, self-esteem, environment, and career)

Study Intervention	Month 0	Month 1	Month 2	Month 3	Month 4	Month 5	Month 6
Informed consent	Х						
SYD intervention – Control Group					Х	Х	Х
SYD intervention – Intervention		Х	Х	Х	Х	Х	Х
Group							
WHOQOL-BREF - Control Group	Х	Х	Х	Х			Х
WHOQOL-BREF - Intervention	Х	Х	Х	Х			Х
Group							
EQ-5D-5L - Control Group	Х	Х	Х	Х			Х
EQ-5D-5L - Intervention Group	Х	Х	Х	Х			Х
HADS - Control Group	Х	Х	Х	Х			Х
HADS - Intervention Group	Х	Х	Х	Х			Х
PSS-4 - Control Group	Х	Х	Х	Х			Х
PSS-4 - Intervention Group	Х	Х	Х	Х			Х

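### The Month 6 comparison of early with more experienced SYD users is not supported by the design, and the protocol is not consistent on Intervention Group use in Months 4-6

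*Protocol*

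**What the plan says.** The protocol describes what the Intervention Group does with SYD in several places.

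- Section 3.5, Intervention Group paragraph: participants are asked to "download / interact with the SYD app (Months 0-3"), and Month 6 is a final assessment.
- Section 8: they "receive intervention / complete monthly assessments in (Months 1-3"), and then "A final assessment will be performed after 3 months (Month 6) to assess longer term effects of the intervention".
- Schedule table (end of section 6, beside the heading of section 7): the row beginning "SYD intervention – Intervention" carries a mark in each of Months 1 to 6. The same mark is used for the Control Group in Months 4 to 6.
- Section 3.5, Design considerations: the first cohort is studied "with SYD as the intervention provided to participants, to engage with, for 3 months as a minimum". One purpose of following it to Month 6 is to see "whether participants voluntarily continue using SYD or not beyond the primary endpoint".
- Section 3.5, Design considerations, on the period after the Control Group starts: the comparison "will allow comparisons of an early (in second cohort) versus a more experienced group (first cohort) using SYD contemporaneously".

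Persistence of the primary endpoint changes to 6 months is secondary objective and endpoint 3 (sections 1, 3.3 and 3.8). After the Control Group starts SYD, both groups complete the questionnaires only once more, at Month 6.

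**The concern.** The Design considerations leave open whether the first cohort goes on using SYD, and then describe a comparison that takes continued use for granted. At Month 6 the Control Group is within the period in which it has been invited to use the app. On the wording of sections 3.5 (Intervention Group paragraph) and 8, the Intervention Group is three months past its own period. If many have stopped, a difference caused by lapse could be reported as an effect of longer experience.

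The same looseness affects secondary endpoint 3. A Month 6 result after use has ended and a Month 6 result under continuing use answer different questions, and the protocol does not say consistently which one it is asking.

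**Working it through.** **1. The statements side by side**

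| Place | What it implies for the Intervention Group in Months 4-6 |
|---|---|
| 3.5, Intervention Group paragraph | Stated SYD period ends at Month 3; Month 6 is follow-up |
| 8 | Same, with the period given as Months 1-3 |
| Schedule table | SYD marked in every month to Month 6 |
| 3.5, Design considerations (minimum) | At least 3 months, no upper limit |
| 3.5, Design considerations (continuation) | Voluntary, to be observed |
| 3.5, Design considerations (contrast) | Use presumed, at the same time as the second cohort |

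The first five rows can be reconciled as three months of requested use followed by optional use with access kept. The sixth does not follow from that reading.

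**2. What differs between the cohorts at Month 6**

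- Time since start: 6 months in the first cohort. In the second it is 6 - 4 = 2 months (start at Month 4, section 6) or 6 - 3 = 3 months (start after 3 months, section 3.5).
- Current use: optional in the first cohort on the reading above, invited in the second.
- Cumulative exposure: depends on both.

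One between-cohort difference cannot separate these three.

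**3. Illustration of size**

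The protocol gives no effect size, SD or usage rate for this comparison, so there is no figure to reproduce. All inputs here are assumed except the 250 evaluable per group (section 3.9). Let d be the effect while using SYD (in SD), k the fraction of d kept after stopping, u1 and u2 the shares of the first and second cohort using SYD at Month 6, and s the share who ever started, taken as equal in both cohorts. Experience is assumed to add nothing.

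Mean benefit in cohort i = d·u_i + k·d·(s - u_i), so first minus second = d·(1 - k)·(u1 - u2).

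With k = 0:

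| u1 | u2 | Difference | d = 0.2 | d = 0.3 | d = 0.5 |
|---|---|---|---|---|---|
| 0.3 | 0.8 | -0.5d | -0.10 | -0.15 | -0.25 |
| 0.5 | 0.8 | -0.3d | -0.06 | -0.09 | -0.15 |
| 0.8 | 0.8 | 0 | 0 | 0 | 0 |
| 0.5 | 0.5 | 0 | 0 | 0 | 0 |
| 0.8 | 0.5 | +0.3d | +0.06 | +0.09 | +0.15 |

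With k = 0.5 every entry halves. At 250 per group the standard error is √(2/250) = 0.0894 SD and the 95% half-width is 1.96 × 0.0894 = 0.175 SD. For the first row, the chance of a difference significant at the two-sided 5% level is about 20%, 39% and 80%, although experience has no effect by construction.

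**4. Persistence within the first cohort**

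Take k = 0 and let use fall from 0.8 at Month 3 to 0.5 at Month 6. The mean benefit goes from 0.8d to 0.5d, so 0.5/0.8 = 62.5% appears to be retained. Yet those who stopped keep nothing and those who continued keep everything. Whether this counts as persistence depends on what the schedule intends for Months 4-6.

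**The case against.** The strongest defence is that the sections do not truly contradict each other. Section 3.5 sets three months as a minimum, nothing says that access ends at Month 3, and section 3.5 keeps access open after the trial. Months 0-3 or 1-3 can then be the requested period and the table marks can be availability. This stands: a reader might infer that the statements cannot all be true, and the documents do not support that. What remains is that no section states this reading, and that under it the claim of contemporaneous use is still unsupported. The trial schema (section 3.6) is not visible and may be clearer, but it would not change the text elsewhere.

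It also stands that the early-versus-experienced contrast is not a listed objective or endpoint, that the trial is described as a pilot, and that section 10.1 counts the longer-term analysis from first interaction with the app. Counting from first use, however, does not say whether use continues.

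Engagement is already a secondary objective, and section 10.1 puts level of interaction into the mixed models, so lapse would probably be seen. But use is observed after randomisation. Adjusting for it does not yield a randomised contrast of experience.

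Finally, a reader might infer that the beginners are bound to look better, or that the difference measures current use alone. Neither follows. The second cohort is also only invited, its use is equally unknown, and time since start and cumulative exposure differ as well.

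**Conclusion.** The point holds in a limited form. The protocol does not state consistently what the Intervention Group is asked to do with SYD in Months 4-6. On the most favourable reading, the Month 6 between-cohort difference still cannot be interpreted as an effect of experience.

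Neither the size nor the direction of any misreading can be fixed from the document. Section 3.9 says that sufficient interaction with SYD cannot yet be predicted. The range of -0.25 to +0.15 SD rests wholly on assumed effects and usage shares, on equal uptake, and on no true effect of experience. Under those assumptions it is zero whenever use is equal in the two cohorts.

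The 3-month between-group comparison is not affected. Priority is minor to moderate, because the point concerns a supporting comparison and the interpretation of secondary endpoint 3.

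**What to change.** 1. Reconcile section 3.5 (Design considerations and Intervention Group paragraph), the schedule table and section 8, so that one statement says what the Intervention Group is asked to do in Months 4-6. Which rule applies is for the trial team to decide.
2. Restate the Month 6 between-cohort comparison as immediate versus delayed offer of SYD, in all randomised participants regardless of use, and drop the claim about experience. This fits section 3.9, which already says that data on all randomised participants will be evaluated.
3. Beside that comparison, report the share of each cohort using SYD in each of Months 4, 5 and 6, from the engagement data already planned.
4. Word the Month 3 to Month 6 persistence result to match the reconciled schedule: an effect after the SYD period, or an effect under continued access.

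The cost is wording in three places and one descriptive table, with no extra participants or assessments. The app-use data are needed for the section 10.1 models in any case. The downside is a more modest claim about experience.
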